- **Aim 2: To determine the feasibility of a peer-supported mobile health physical activity intervention (*Compañeros con Parkinson's*) for exercise in Latinx people with PD.** We will examine: (2A) intervention engagement, as measured by attendance at exercise classes and with the number of peer contacts (2B) acceptability, (2C) appropriateness, (2D) feasibility and (2E) cultural relevance through self-report surveys and qualitative interviews with study participants.
- **Exploratory Aim: To determine the effects of the peer-supported mobile health physical activity intervention on physical activity** (objectively measured physical activity through the activity monitor), **motivation** (Behavioral Regulation in Exercise Questionnaire), **quality of life** (Parkinson Disease Questionnaire-39 (PDQ-39)), **depression** (Geriatric Depression Scale (GDS)), **apathy** (Lille Apathy Rating Scale (LARS)) and **self-efficacy for physical activity** (Self-Efficacy for Physical Activity (SEPA)).

Study Design: This is a prospective feasibility trial, single group pre-posttest design.

Sample size and justification

This study aims to enroll 20 participants. For this feasibility study, the sample size is comparable to other feasibility trials in populations of individuals with Parkinson disease (Lima & Rodrigues-de-Paula, 2013; Ellis et al., 2013, Colón-Semenza et al., 2018)^{17,19,20}. This sample size will allow for a comparison in feasibility, acceptability, and appropriateness within and across groups. This sample will allow for identifying trends and preliminary efficacy for this intervention. This study will help to inform an appropriate sample size to adequately power larger samples in future studies.

SELECTION AND ENROLLMENT OF PARTICIPANTS

Characteristics of the Study Population: We will recruit 20 Hispanic male, female or non-binary adults age 50+ with Parkinson's Disease. Participants must have the ability to speak, read and write in Spanish or English.

We will use the Recruitment and Community Engagement Core of the UConn Center on Aging. The Core provides a centralized infrastructure for the recruitment of older research volunteers from the community. Recruitment of subjects will be carried out by several mechanisms, Including:

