- e. How can I help someone else living with Parkinson's disease?

There will then be a synchronous virtual meeting that is led by the research team to review the content of the first 6 videos. (approximately 30 - 45 minutes)

The additional 6 videos will cover the following topics related to peer and social support:

- f. Active listening
- g. Creating SMART goals for exercise

- h. Checking in: getting feedback on exercise goals
- i. Identifying facilitators for exercise
- j. Problem-solving and overcoming barriers to exercise
- k. Family and community support for exercise

There will then be a second synchronous virtual meeting, led by the research team, to review the content of the last 6 videos to ensure comprehension and baseline knowledge. (approximately 30 - 45 minutes)

There will be a final synchronous meeting to review check-off sheets that will guide weekly discussions and a knowledge check will be completed through a brief quiz. (approximately 30 - 45 minutes)

Peer-supported mobile health physical activity intervention (*Compañeros con Parkinson's*)

All participants will be peer partners (supporters). Individuals will be matched with a peer of the same gender. Attempts will be made to match those with additional similar traits, such as age, physical activity level, work status, and country of origin. Participants in each matched pair will support one another as they both strive to improve their physical activity.

After participants have completed the training, they will receive a commercially available activity tracker (Fitbit Inspire 2) and instructions on its use. They will wear this activity tracker for the duration of the 8-week period except for showering/bathing. Peers will download the FitBit application on their smart phone or tablet. Participants will be asked to log in to the FitBit app daily to sync their data with the app. If they do not have a smartphone or tablet, one will be provided to them, along with a data plan for the duration of the study. They can choose to have assistance with downloading the app from a research assistant. They can receive basic training on its use with the support of a research assistant via a telephone call or virtual meeting.

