Peers will become “FitBit Friends/*Amigos*” through the FitBit application. Peer pairs will be able to see each other’s accumulated steps over the week and communicate as a pair. This will connect 2 participants into a peer pair. Peer pairs can provide social support to each other through the app with comments and emojis. Participants will be asked to open the FitBit app daily to sync their data with the app. Additionally, peer pairs will establish a weekly meeting schedule by telephone or virtual meeting platform. Weekly meetings will be guided by check-off sheets to ensure critical content is covered and discussion of goal status is completed. Participants will be encouraged to participate in a weekly bilingual virtual exercise class that is synchronous.

In addition, all participants will join a FitBit closed group of *all* participants in the study. This group will be created by the research team and is not publicly available to others. It will be moderated by a research assistant and daily informational and motivational content will be posted. Participants can provide social support to each other in the group through the app with comments and emojis.

Weekly Meeting Calls Topics of Discussion (approx. 15- 30-minute discussions, 1x/week for 8 weeks)

1. Getting acquainted and building rapport; identifying core values; becoming “FitBit friends/*amigos*”
2. Establishing SMART goal (short-term/weekly and overall/8 week) and tying in with core values
3. Action Plan (Goal Check)
4. Benefits of Exercise (Goal check)
5. Feedback on Goals (Goal Check)
6. Facilitators/Barriers of Exercise (Goal check)
7. Family Support for Exercise/ Local and National Exercise Resources (Goal check)
8. Re-establishing goals/Sustaining exercise/Wrap up (Goal check)

A research assistant will call participants each week to determine if the weekly peer interaction call has been completed, to assist with any barriers to peer connection, and to assess technology needs. The research assistant will also assess for adverse events during this call. The RA will be guided by the adverse events form.

Support for an increase in physical activity

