To support an increase in physical activity, participants will have access to a weekly virtual synchronous bilingual exercise class that is geared towards the needs of people with PD. The class will have 3 areas of focus: aerobic exercise, resistance exercise (using body weight), and balance, breathing, and stretching exercise. The first 3 weeks will focus on aerobic exercise, the second 3 weeks on resistance training and the last 2 weeks will focus on balance, breathing and stretching exercise. All exercise classes will be tailored to the needs of people with PD and designed by a physical therapist with a specialization in neurologic physical therapy (PI-[name]) and a fitness instructor with a certificate from the American Parkinson Disease Association for Fitness Professionals. The instructor will provide modifications of the exercises so that individuals can participate at the level that is suited to their status.

Outside of the exercise class, participants will be encouraged to increase their walking and general physical activity. For example, peer pairs may develop a goal to increase their steps by 1,000 steps/day and may develop a plan to march in place during commercials when watching their favorite television show.

Post-assessment

Baseline measures will be repeated at the conclusion of the intervention as presented above. They will include:

- a. **Physical Activity Scale for the Elderly**
- b. **Behavioral Regulation in Exercise Questionnaire-2**²¹⁻²³
- c. **Parkinson Disease Questionnaire-39 (PDQ-39)**²⁴
- d. **Self-Efficacy for Physical Activity (SEPA)**^{25,26}

e. GDS-15

f. LARS

Participants will receive a phone call to complete the aforementioned assessments.

In addition, the following surveys, **Acceptability of Intervention Measure (AIM)**, **Intervention Appropriateness measure (IAM)**, and **Feasibility of Intervention Measure (FIM)** will be completed via ReDCAP. (If individuals are unable to complete the survey online, they will receive a physical copy of these surveys through standard mail with a self-addressed envelope to return to the research team.) Each measure has 4 items that assess acceptability, appropriateness, and feasibility, respectively. They are constructed at a 5th grade reading level with a Likert scale that ranges from completely agree to completely disagree. Validity (α from 0.85-0.91) and reliability (0.73-0.88) were high for all three scales.²⁵ (approximately 15 minutes to complete all 3 surveys)

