Content and thematic analysis of qualitative data; descriptive statistics to characterize the sample and measure feasibility.

- Aim 1 analysis
 - Scores equal to or greater than 75% on the Acceptability of Intervention Measure (AIM), Intervention Appropriateness measure (IAM), and Feasibility of Intervention Measure (FIM) are set to determine acceptability, appropriateness, and feasibility of the peer partner training.
 - Cultural relevance of the peer partner training will be determined through content analysis of focus group discussions
- Aim 2 analysis
 - Peer engagement will be successful if connecting $\geq 80\%$ of the recommended times over the course of the intervention period.
 - Scores equal to or greater than 75% on the Acceptability of Intervention Measure (AIM), Intervention Appropriateness measure (IAM), and Feasibility of Intervention Measure (FIM) are set to determine acceptability, appropriateness and feasibility of the peer partner intervention.
- Exploratory aim analysis
 - Group means will be compared from baseline to post-intervention using paired t-tests to assess change in physical activity levels (Physical Activity Scale for the Elderly & objectively measured physical activity through the activity monitor), motivation (Behavioral Regulation in Exercise Questionnaire), quality of life (Parkinson Disease Questionnaire-39 (PDQ-39)), depression (GDS), apathy (LARS) and self-efficacy for physical activity (Self-Efficacy for Physical Activity (SEPA)).

Dissemination: The results of this research will be disseminated at a professional conference in a poster or platform presentation. After receiving feedback from this presentation, results will be disseminated in a peer-

reviewed scholarly journal. Additionally, if the results from this research are promising, it will be used to inform a randomized controlled trial of the intervention.

PROTECTION OF HUMAN SUBJECTS

Risks to Human Subjects:

Physical Risk

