The FitBit data will be housed on the FitBit device and might be subject to a loss of confidentiality. Only those that have the email and password for the FitBit account will have access to this data. This data will be downloaded to an encrypted and password protected UConn computer during the course of the study. Once the study is over the password will be changed so that only the individual has access to their FitBit data.

Participants will be matched with another person with PD and communicate with this person once per week during a virtual meeting. Participants will be FitBit friends and see each other's steps per week. There is a risk of conflicts between the peer partners. One person in the peer pair may drop out of the study. We will attempt to create a successful match by matching peers with others with similar characteristics (age, retired

vs working, stage of the disease, etc.). If there is a conflict between peer partners, a research assistant will be available to meet with the pairs to help resolve the conflict. If a peer partner drops out, we will attempt to reassign the participant to another partner.

Other risks

Survey administration may make participants feel uncomfortable answering some of the questions. Participants will be instructed that they can choose not to answer any questions that make them feel uncomfortable.

References:

3. Alberts JL, Rosenfeldt AB. The Universal Prescription for Parkinson's Disease: Exercise. *J Parkinsons Dis*. 10(Suppl 1):S21-S27. doi:10.3233/JPD-202100

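### The exploratory paired t-tests treat 20 change scores as independent although the intervention runs in mutually supporting peer pairs, and the plan has no pair-level analysis

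*Combined protocol and SAP*

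**What the plan says.** Under Study Design the protocol states: "This is a prospective feasibility trial, single group pre-posttest design". Twenty participants are planned. All of them act as peer partners, matched two by two within gender. The section on the peer-supported intervention says: "Participants in each matched pair will support one another as they both strive to improve their physical activity". On matching it adds: "Attempts will be made to match those with additional similar traits, such as age, physical activity level, work status, and country of origin". Through the app, partners see each other's "accumulated steps over the week and communicate as a pair", and they hold one guided call a week for 8 weeks that covers goal setting and goal checks. Under Support for an increase in physical activity: "For example, peer pairs may develop a goal to increase their steps by 1,000 steps/day".

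Under METHOD(S) OF DATA ANALYSIS, the exploratory aim has one method: "Group means will be compared from baseline to post-intervention using paired t-tests to assess change in physical activity levels". The same sentence applies it to motivation, quality of life, depression, apathy and self-efficacy. No pair-level summary, pair term or within-pair correlation is mentioned. The Informational Risk section foresees that pairs may break: "If a peer partner drops out, we will attempt to reassign the participant to another partner". It does not say how such participants are analysed.

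**The concern.** The word paired in the analysis section refers to two measurements on one person, not to two partners. Once each person is reduced to a change score, the test is a one-sample t-test on 20 values assumed independent. The intervention is built to make partners influence each other, most directly on physical activity. If partners tend to improve or fail together, 20 change scores carry less information than 20 unrelated ones, and the computed standard error is too small.

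The feasibility thresholds (75% on the three implementation measures, 80% of recommended peer contacts) do not use these tests, and no stated go/no-go rule depends on them. However, the sample size section says: "This sample will allow for identifying trends and preliminary efficacy for this intervention". It also expects the study to inform the size of later ones, and the dissemination paragraph says promising results would inform a randomized trial. Confidence intervals that are too narrow would make that evidence look firmer than it is. A later trial of the same paired intervention would also need a within-pair correlation, which this plan does not report.

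**Working it through.** **Inputs.** From the documents: n = 20, cluster size 2, hence 10 pairs if everyone is paired and completes. Assumed, because the documents are silent: two-sided 5% test, normal change scores, and a within-pair correlation of change (ICC, ρ) from -0.2 to 0.5. The plan states no alpha, power, effect size or SD, so there is no figure of its own to reproduce.

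**Standard error.** With σ the SD of change and 10 pairs:

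- True variance of the mean change: (σ²/20)(1 + ρ).
- Expected value of the sample variance used by the t-test: σ²(1 − ρ/19).
- True SE divided by SE used: √[(1 + ρ)/(1 − ρ/19)].
- Effective n: 20/(1 + ρ).

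For ρ = 0.3: √(1.3/0.9842) = 1.15, and 20/1.3 = 15.4. The person-level SD is hardly affected: √0.9842 = 0.992, or 0.8% low. The error therefore lies almost wholly in ignoring the covariance between partners.

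**Type I error.** Simulated under no mean change (400,000 data sets per ρ). The person-level test has 19 df (critical value 2.093); the pair-mean test has 9 df (2.262).

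| ρ | True SE / SE used | Effective n | Planned test | Pair-mean test |
|---|---|---|---|---|
| -0.2 | 0.89 | 25.0 | 3.0% | about 5% |
| 0 | 1.00 | 20.0 | 5.0% | about 5% |
| 0.1 | 1.05 | 18.2 | 6.1% | about 5% |
| 0.2 | 1.10 | 16.7 | 7.3% | about 5% |
| 0.3 | 1.15 | 15.4 | 8.6% | about 5% |
| 0.5 | 1.24 | 13.3 | 11.2% | about 5% |

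The pair-mean test stays between 4.9% and 5.1% in every row.

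**Two broken pairs** (8 pairs plus 2 single participants, n = 18). The planned test gives 7.1%, 8.2% and 10.5% at ρ = 0.2, 0.3 and 0.5. A t-test on the 10 cluster means gives 4.9% to 5.1%.

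**Price of the pair-mean test if ρ = 0.** The 95% CI multiplier rises by 2.262/2.093 = 1.08, about 8%. The planned test on 20 people has 80% power at a standardized change of 0.66. At that effect (noncentral t):

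| Complete pairs | Person-level power | Pair-mean power |
|---|---|---|
| 10 | 80% | 75% |
| 9 | 75% | 69% |
| 8 | 69% | 62% |

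If ρ is 0.2, 0.3 or 0.5, pair-mean power with 10 pairs is 67%, 64% or 58%. Here the pair-mean test reflects the information actually present.

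**How well 10 pairs estimate ρ.** For an observed ρ of 0.3, F = 1.3/0.7 = 1.857 on 9 and 10 df. The F limits 3.779 and 3.964 give 1.857/3.779 = 0.491 and 1.857 × 3.964 = 7.361. Applying (F − 1)/(F + 1) gives a 95% CI from -0.34 to 0.76. At a true ρ of 0.2 the ANOVA estimate is negative with probability P(F < 0.8/1.2) = 28%; at 0.3, with probability 18%. A random intercept confined to non-negative variance would often be estimated at zero and fall back on the independence analysis.

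**The case against.** The strongest case against acting is that the harm is conditional and modest. With clusters of two, variance inflation is only 1 + ρ. At ρ of 0.1 to 0.2 the true SE is 5% to 10% above the one used, and nothing in the documents supports 0.3 to 0.5. Even the sign is open: matching beyond gender is only attempted and acts on baseline traits, the joint step goal is an example, and the background names competition among the peer mechanisms. For mood, apathy and quality of life the route to correlation is weaker than for steps. Other features limit an efficacy reading more: there is no control group, and at least seven outcomes are tested with no multiplicity rule (if independent, 1 − 0.95⁷ = 30% chance of at least one false positive).

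All of this stands and limits the point to one of moderate weight. It does not show that the planned standard error is right: that holds only at ρ = 0, and the plan gives no reason to expect zero. A pair-level test needs no guess about ρ.

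A further objection concerns the remedy. If pairs break, an unweighted mean over clusters gives a lone participant twice the weight of a paired one. With 8 pairs and 2 singles, a single counts 1/10 and a paired member 1/20, against 1/18 each at person level. That shifts the estimate towards people who lost a partner. Type I error stays near 5%, but the plan should acknowledge the change in what is estimated, or use the model-based alternative.

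**Conclusion.** The concern holds. The exploratory tests assume independence between people whom the design deliberately links, and no other section corrects for it. Under the assumptions above (10 complete pairs, two-sided 5%), actual type I error runs from about 6% at a within-pair correlation of 0.1 to about 11% at 0.5. It is correct at zero and conservative below zero. A positive value is plausible, most of all for physical activity, but not established. The mean change is unaffected when all pairs are complete; what is wrong is its standard error, interval and p-value. The feasibility conclusions are untouched. The analysis should be changed, but the point does not threaten the trial's main purpose.

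**What to change.** In the exploratory aim analysis:

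- Make the peer pair the unit. The simplest form is a one-sample t-test on pair-mean changes (9 df with 10 pairs), valid for either sign of the correlation. The alternative is a model for change with pair-level correlation, small-sample degrees of freedom and freedom for that correlation to be negative.
- Before data are seen, state a rule for broken and reassigned pairs. One option: everyone linked as partners at any time forms one cluster, and a participant whose partner has no post-intervention data and who is not reassigned forms a cluster of one. Say how unequal clusters are weighted.
- Report mean changes with 95% CIs, and the within-pair correlation with its interval, noting that about 10 pairs estimate it imprecisely.
- Note that the all-participant FitBit group and the shared exercise class may add dependence that a pair-level analysis does not remove.

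This takes a few lines of text and no new data, since the study already holds the pair identities. The statistical cost, if partners' changes are in fact uncorrelated, is the 8% larger interval multiplier and the 5 to 7 points of power shown above.
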